### **Inclusion criteria:**

- Sixty-six Male and female subjects with SIS and age between 20-50 (**Cools et al., 2012**).
- body mass index (BMI)<20 kg/m^2 (**Celik et al., 2012**).
- subjects complaining secondary Shoulder impingement (**Cools et al., 2012**).
- subjects with altered scapular resting positions and dyskinesia (**Cools et al., 2007; 2003**).
- Subjects will be included if they met at least 2 of the following 5 criteria:

**(1) Neer's Impingement Test:** The patient's arm is passively and forcibly fully elevated in the scapular plane with the arm medially rotated by the examiner (**Fig. 8**). A positive Neer impingement sign is present if pain is produced when the arm is forcibly flexed (**Magee and Manske, 2020**).

**Figure 2 Neer's Impingement Test**

**(2) Hawkins-Kennedy Impingement Test:** The examiner forward flexes the arm to 90 and then forcibly medially rotates the shoulder (**Fig.9**). Pain indicates a positive test result for supraspinatus tendinosis or secondary impingement (**Magee and Manske, 2020**).

[figure not shown]
**Figure 3 Hawkins-Kennedy Impingement Test**

**(3) Supraspinatus (“Empty Can” or Jobe) Test:** The patient’s arm is abducted to 90 with neutral (no) rotation, and the examiner provides resistance to abduction. The shoulder is then medially rotated and angled forward 30 (“empty can” position) so that the patient’s thumbs point toward the floor (**Fig. 10**) in the plane of the scapula. Resistance to abduction is again given while the examiner looks for weakness or pain, reflecting a positive test result (**Magee and Manske, 2020**).

**Figure 4 Supraspinatus (“Empty Can” or Jobe) Test**

**(4) Apprehension and relocation Tests:** The examiner abduct the arm to 90 and laterally rotates the patient’s shoulder slowly (**Fig11**). A positive test result is indicated by a look or feeling of apprehension or alarm on the patient’s face and the patient’s resistance to further motion. If the apprehension test result is positive, the examiner then applies a posterior translation stress to the head of the humerus (relocation test). The test result is considered positive if the patient loses the apprehension, pain decreases, and further lateral rotation is possible before the apprehension or pain returns (**Magee and Manske, 2020**).

**Figure 5 Apprehension and Relocation Tests**

## **Exclusion criteria**

Patients will be excluded if they had any of the following conditions: (Cools et al., 2012).

- Undergone shoulder surgery.
- Exhibited symptoms related to the cervical spine
- Taking nonsteroidal anti-inflammatory medications
- Received a steroid injection in the past 12 months
- Were already enrolled in a physical therapy program

## **Assessment Instrumentation**

The following tools will be used for assessment:

- 1- Hand-held dynamometer.
- 2- isometric strength testing.
- 3- Modified Lateral Scapular Slide test
- 4- shoulder pain and disability index.

## Hand-held dynamometer (HHD):

Hand-held dynamometer (Model 01165, Lafayette Instrument Company, Indiana) (**figure 12**). is an easy and reliable device to assess isometric muscle strength for shoulder and scapular muscles in both clinical and research settings, (ICCs) ranged from .77 to .99 in healthy subjects and from .75 to .99 in patients with impingement, for all muscle groups except the upper trapezius ( $P < .05$ ).

Reliability values ranged from good to high in healthy subjects but were less consistent for the upper trapezius (ICC .45–.65). The relationship with BMI and muscle strength illustrates that as BMI increases, there is a decrease in reliability values of the upper trapezius (ICC = .35–.65) (Celik et al., 2012)

Figure 6 Lafayette Handheld dynamometer (Adopted from Celik et al., 2012).

## Isometric strength imbalance of shoulder girdle muscles:

Isometric strength imbalance of shoulder girdle will be examined bilaterally. Subject will perform four scapular muscle tests (SA, UT, MR and LR). Then agonist and antagonist ratio of UT/SA, and MR/LR will be

[figure not shown]

calculated. Hand held dynamometer (HHD) will be used to record the amount of maximum muscle force applied by the subject during the muscle test.

### **Lateral Scapular Slide test**

The lateral scapular slide test (LSST) (**Kibler, 1998**) is reliable in screening scapular position. used to determine scapular involves measuring the distance from the inferior angle of the scapula to the nearest vertebral spinous process using a tape measure or goniometer in three positions: shoulder in neutral, shoulder at 45 degrees of coronal plane abduction with hands resting on hips, and the shoulder at 90 degrees abduction with the arms in full internal rotation (**figure 13**).

Overall ICC ranged from .83 to .96. The coefficients of determination ranged from .38 to .89. The SEM ranged from 3.00 to 8.26 mm LSST provides more objective measures than pure observation (**Curtis et al., 2006**).

**Figure 7 Lateral scapular slide test. The examiner measures from the spinous process to the scapula at the level of the base of spine of the scapula**

## **Shoulder pain and disability index (Appendix II):**

Self-report questionnaire developed to measure the pain and disability associated with shoulder pathology. The SPADI consists of 13 items in two subscales: pain (five items) and disability (eight items).

The pain dimension consists of five questions regarding the severity of an individual's pain. Functional activities are assessed with eight questions designed to measure the degree of difficulty an individual has with various activities of daily living that require upper-extremity use. The SPADI takes 5 to 10 minutes for a patient to complete and is the only reliable and valid region-specific measure for the shoulder **(Roash al., 1991)**.

Patients asked to mark the appropriate point on the scoring system of the questionnaire, which represented their status of shoulder pain and disability. Total pain score:  $/ 50 \times 100 = \%$ , Total disability score:  $/ 80 \times 100 = \%$  and Total SPADI score:  $/ 130 \times 100 = \%$  Higher score on the SPADI is indicative of higher pain and/or disability **(Breckenridge al., 2011)**.

Psychometric Properties the SPADI :MDC: 18 point (MDC 95%) with  $ICC \geq 0.89$ , The MCID has been reported to be 8 points; this represents the smallest detectable change that is important to the patient **(Paul et al 2004)**.

No large floor or ceiling effects for the SPADI have been observed **(Bot et al 2004, Roy et al 2009)**.

### **Procedures:**

The participants will be interviewed and details and importance of the study will be discussed with them. Participants who agree to share in the study

will sign a written consent form (**Appendix I**). After that the following procedures will be conducted

## **Assessment procedure**

Assessment procedure will be performed before and after the treatment. The following procedure will be conducted

### **1. Measuring isometric strength with HHD**

The HHD will be used to record the amount of resistance (in kilograms) applied by the examiner during the 4 scapular muscle tests as shown in **Figures 14 to 17**.

Muscle testing will be performed by first pre-positioning the scapula in the midrange position of scapular motion for the specific muscle test. The midrange position will be located by having the subject go through the available scapular range of motion, and then the midrange will be estimated as the midpoint of the motion.

This midrange position will be selected to optimize the length-tension relationship of the tested muscle and, therefore, the generation of a maximum isometric contraction (**Michener et al., 2005**).

The subjects will be instructed to maintain the midrange position during each muscle test as resistance was gradually applied via the HHD until the examiner matches the subject's effort (**Michener et al., 2005**).

The LT muscle test will be performed as described by Hislop et al. (**1995**) with the resistance force from the HHD being applied to the spine of the scapula

midway between the acromial process and the root of the spine, as shown in **Figure 14**.

**Figure 8 Lower trapezius muscle test.**

The force on the scapula will be applied in the superior and lateral direction parallel to the long axis of the humerus, which will be at 140 degrees of elevation. The scapular motion for this test is scapular adduction and depression.

The SA muscle test will be performed as described by Kendall et al., (1993). The original test described resistance applied against the subject's closed fist. For this study, the elbow will be placed in 90 degrees of flexion, and resistance will be applied to the ulna at the olecranon process along the long axis of the humerus.

The triceps muscle will be monitored visually and by palpation to ensure that it does not contribute to force production during the SA muscle test. The scapular motion for this test was scapular protraction **Figure 15**.

**Figure 9 Serratus anterior muscle test.**

The MT muscle test will be performed as described by Hislop et al. (1995). The HHD resistance force will be applied to the spine of the scapula midway between the acromial process and the root of the spine, as shown in **Figure 16**.

The force will be applied in the lateral direction parallel to the long axis of the humerus, which will be placed in 90 degrees of abduction. Scapular retraction was the scapular motion for the MT muscle test **Figure 16**.

**Figure 10 Middle trapezius muscle test.**

The UT muscle test will be performed as described by Hislop et al. (1995). The HHD will be placed over the superior scapula. Force will be applied directly downward (inferior) through the HHD in the direction of scapular depression. Scapular elevation will be the scapular motion for the UT muscle test **Figure 17**.

**Figure 11 Upper trapezius muscle test.**

All subjects will perform the muscle tests in the same order: LT, SA, MT, and UT muscle tests. The examiner will not view the digital readout on the HHD during performance of the muscle test. After the muscle test is completed, the examiner then will view the kilograms and recorded the information on a data recording sheet. Each muscle test will be performed 3 times consecutively, and the average will be used for data analysis.

## **2. Isometric strength imbalance of shoulder girdle muscles**

Isometric strength imbalance of shoulder girdle will be examined bilaterally. Based on the muscle test results from the previous measurement, The ratio of UT/SA and MR/LR will be calculated.

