In patients diagnosed with rotator cuff tendinopathy, intermuscular coordination between the lower trapezius and serratus anterior, as well as between the lower trapezius and upper trapezius is disrupted in arm elevation tasks, indicating two altered ratios and the importance of the muscle function (**Michener et al., 2016**). Alterations in scapular muscle performance have been found in subjects with scapular dyskinesia. Hyperactivity of the upper trapezius (UT) with reduced middle (MT) and lower trapezius (LT) muscle activation in addition to insufficient serratus anterior (SA) muscle function have been related to decreased amounts of scapular upward rotation, external rotation, and posterior tilt in patients (**Ludewig et al., 2010**).

Research into scapular stability exercises for the management of SIS is increasing, yet there is little evidence on their efficacy (**Ginn and Cohen, 2005**). Interventions focused on reducing scapular dyskinesia compared to just stretching and strengthening exercises result in significantly better shoulder disability measures (**Moura et al., 2016; Struyf et al., 2013**). The addition of scapular stabilization exercises to stretching and strengthening exercises can be significantly beneficial in increasing the strength, developing joint position sense and decreasing dyskinesia (**Baskurt et al., 2011**).

Proprioceptive neuromuscular facilitation (PNF) is a rehabilitation concept which is widely used by physical therapists (**Westwater-Wood et al., 2010; Smedes et al., 2016**), promoting motor learning, motor control, strength and mobility

(IPNFA, 2019; Smedes et al., 2016). This comprehensive rehabilitation approach includes task-oriented training with manual facilitation aimed at motor learning and motor control (Adlers et al., 2014; Smedes et al., 2016). Also, PNF positions improve movement efficiency of the joint by inducing changes in the muscle activation sequence (Shimura and Kasai, 2002) and it reportedly helps in the early recovery of the patients with SIS (Nakra et al., 2013).

To the authors' knowledge, none of the studies has investigated the potential effect abnormal scapular muscle strengthening versus PNF exercise on the muscle strength, muscle ratio, and ROM of the scapula during arm elevation in patient with SIS.

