**Figure 20 SCAPULAR ANTERIOR DEPRESSION**

## **Statistical analysis**

- Data will be analyzed using the statistical package for social science (SPSS) program, version 27 (SPSS Inc, Chicago, IL, USA).
- Descriptive statistics will be used to summarize the data. Data will be reported as mean  $\pm$  SD for quantitative variables and frequency distribution (%) for categorical variables.
- The normality of data will be checked using Shapiro–Wilk test.
- Levene’s test will be used to check the homogeneity between groups.
- Two-way Multiple Analysis of Variance (MANOVA) will be conducted to compare the mean values of the measured variables of the three groups.
- The level of significance for all statistical tests will be set at  $\alpha = 0.05$ .

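### The ratio procedure covers only one of the three hypothesised muscle ratios: UT/LT and UT/MT are not listed, and MR/LR, which is listed, has no hypothesis

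*Protocol*

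**What the plan says.** The Protocol's *Purpose of the study* and *Research question* both include scapular muscle ratio as an outcome. *Hypotheses of the study* makes this specific in three of its twelve items: hypothesis 5 is on UT/LT, hypothesis 6 on UT/MT and hypothesis 7 on UT/SA.

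Two places say which ratios will be worked out, and they agree with each other:

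- *Assessment Instrumentation*, under *Isometric strength imbalance of shoulder girdle muscles*, lists the tests: "Subject will perform four scapular muscle tests (SA, UT, MR and LR". It continues: "Then agonist and antagonist ratio of UT/SA, and MR/LR will be" calculated.
- *Assessment procedure*, item 2, says: "Based on the muscle test results from the previous measurement, The ratio of UT/SA and MR/LR will be calculated".

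The measurement that item 2 draws on is item 1, *Measuring isometric strength with HHD*. It describes four tests under other labels: "All subjects will perform the muscle tests in the same order: LT, SA, MT, and UT muscle tests". It also fixes the value to be used: "Each muscle test will be performed 3 times consecutively, and the average will be used for data analysis".

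*Statistical analysis* then says that a MANOVA "will be conducted to compare the mean values of the measured variables of the three groups", without listing those variables.

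**The concern.** The hypotheses and the procedure give two different lists for the same outcome. Someone following the procedure would calculate UT/SA and MR/LR. Hypotheses 5 and 6 would then have no calculated outcome, and the data set would hold a ratio that no hypothesis mentions.

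The two omitted ratios are the ones closest to the trial's rationale. The *Introduction* describes the problem as "Hyperactivity of the upper trapezius (UT) with reduced middle (MT) and lower trapezius (LT) muscle activation", an imbalance of the upper trapezius against the middle and lower parts. UT/MT and UT/LT are the strength ratios that correspond to it.

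While both lists stand, the choice of ratios to report could be made after the results are known. The statistical section does not say which list governs.

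**Working it through.** There is no published figure to reproduce. The check sets the two lists side by side under each plausible meaning of MR and LR.

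**Inputs**

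- Hypothesised ratios (*Hypotheses of the study*, 5 to 7): {UT/LT, UT/MT, UT/SA}.
- Ratios to be calculated (*Assessment Instrumentation* and *Assessment procedure*, item 2): {UT/SA, MR/LR}.
- Muscles tested (*Measuring isometric strength with HHD*): {LT, SA, MT, UT}.

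MR and LR are not defined in the protocol text I could read. An abbreviation list in the front matter, which I have not seen, might define them, so the check does not depend on their meaning.

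**Comparison**

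| Reading of MR/LR | In both lists | Hypothesised, not in procedure | In procedure, no hypothesis |
|---|---|---|---|
| Literal (undefined) | UT/SA | UT/LT, UT/MT | MR/LR |
| Slip for MT/LT (assumption) | UT/SA | UT/LT, UT/MT | MT/LT |
| Medial/lateral rotation (assumption) | UT/SA | UT/LT, UT/MT | MR/LR |

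Each row gives 1 of 3 hypothesised ratios covered and 2 of 3 not. The lists hold 3 + 2 = 5 entries with 1 shared, so together they name 4 distinct ratios.

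**Could MT/LT stand in for hypotheses 5 and 6?** No:

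MT/LT = (UT/LT) ÷ (UT/MT)

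UT cancels. With assumed strengths of UT 10, MT 5 and LT 4 kg, UT/MT = 10/5 = 2.0, UT/LT = 10/4 = 2.5 and MT/LT = 5/4 = 1.25. If UT alone falls to 8 kg, UT/MT = 8/5 = 1.6 and UT/LT = 8/4 = 2.0, both 20% lower, while MT/LT stays at 1.25. The strengths are invented for illustration; the cancellation holds for any values.

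**Can the missing ratios be recovered?** Yes. UT/LT, UT/MT and UT/SA use only UT, LT, MT and SA, and all four are tested, with the average of three trials retained. Coverage goes from 1 of 3 to 3 of 3 with no new measurement.

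**The case against.** The strongest reply is that little is lost. The procedure does not say that its list is exhaustive, the hypotheses themselves name the ratios, and every component is measured. On this view only a linking sentence is missing. The practical part of this stands: no data are lost, and the point is a correction to the text rather than a threat to the trial. It does not remove the contradiction. Both places that say what will be calculated give the same other pair, so it is not a single typing error, and nowhere does the text say that UT/LT or UT/MT will be derived.

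A second reply is that the variables entering the MANOVA are commonly left to the statistical analysis plan. That is fair, and the unspecific wording of the statistical section is not counted as a fault here. The point rests only on the conflict between the hypotheses and the ratio sections.

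A third reply is that MR and LR may mean medial and lateral rotation, a movement vocabulary the protocol uses elsewhere. This fits poorly, because item 2 takes its ratios from the preceding measurement, which consists of the four scapular tests. The count would still be 1 of 3. It would, however, mean that MR/LR itself could not be formed from the tests described, so the claim that no new test is needed covers the three hypothesised ratios and not necessarily MR/LR.

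**Conclusion.** The concern holds. The ratio procedure covers 1 of the 3 hypothesised ratios (UT/SA), omits 2 (UT/LT and UT/MT), and adds 1 (MR/LR) that has no hypothesis and whose labels match no described test. This does not depend on what MR and LR stand for: under all three readings considered, hypotheses 5 and 6 have no matching ratio in the procedure. The consequence is limited to outcome definition, since all four component strengths are recorded. It should be corrected, and before the data are analysed, so that the choice of ratios cannot follow the results.

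**What to change.** - In *Assessment Instrumentation*, name the four tests UT, MT, LT and SA, as *Measuring isometric strength with HHD* does.
- There and in item 2 of *Assessment procedure*, state that UT/LT, UT/MT and UT/SA will be calculated from the three-trial averages.
- Delete MR/LR. If the sponsor wants to keep it, define it and label it as an additional ratio without a hypothesis.

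The cost is wording in two sections, with no new test, no extra data and no change to the sample size. The one exception is if MR/LR is kept and turns out to mean something other than the muscles already tested; that test would then have to be described.

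A separate small correction can be made at the same time: hypotheses 9 and 10 name motor control exercise as the comparator, where hypothesis 8, on the same outcome, names PNF, the treatment given to Group B. It changes no analysis and is not part of the count above.

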## **3. Lateral Scapular Slide test**

Subjects will be standing with both arms at the sides, in glenohumeral joint neutral. The inferior-most aspect of the inferior angle of the scapula and the adjacent spinous process of the reference vertebra in the same horizontal plane will be identified through palpation and will be marked with marker pen by the examiner as shown in **Figure 18**.

For test position 2 – subject will actively place both hands on the ipsilateral hips (in medial rotation) at 45° of abduction in the coronal plane **Figure 19**.

Position 3 - subject will actively extend both elbows and place the upper extremities in a position of maximum medial rotation at 90° of abduction in the coronal plane **Figure 20**.

[figure not shown]
Measurements will be taken with a vernier caliper from the inferior angle of scapula to adjacent spinous process of reference vertebra. The examiner will obtain the measurements bilaterally.

**Figure 12 LSST position 1- arm at the sides**

**Figure 13 Position 2 both hands on ipsilateral hips**

**Figure 14 Position 3 of abduction 90° and medial rotation**

#### **4. Shoulder pain and disability index**

Patients is asked to circle the number that best describes his/her level of pain or dysfunction of the questionnaire (**Appendix II**). This represents their status of shoulder pain and disability. Total pain score: / 50 x 100 = %, Total disability score: / 80 x 100 = % and Total SPADI score: / 130 x 100 = % Higher score on the SPADI is indicative of higher pain and/or disability

This index will be scored before and after the treatment procedure to measure the function and pain on patients with SIS.

## **Treatment procedure**

[figure not shown]
Group (A) will have scapular muscle training and group (B) will have a scapular PNF program and Group (C) will be a control group will not receive any treatment. Both groups A and B will receive 18 therapy visits (3 sessions per week for 6 weeks).

### **Group (A) Scapular muscle strengthening**

The following four exercise will be performed according to **Cools et al. (2007)**: (1) side-lying forward flexion, (2) side-lying external rotation, (3) prone horizontal abduction with external rotation, and (4) prone extension in neutral position (**Figure 21**).

Before starting the program, the patient will be thoroughly instructed in the four exercises, and illustrations with specific exercise instructions will be provided, as well as a compliance log. All subjects will perform the exercises with the affected side for three sets of 10 repetitions for each exercise, with a 1-minute rest between sets. The exercises are described in (**table 1**)

**Figure 15** the proposed scapular strengthening program

[figure not shown]
**Table 1.** Description of the scapular training program

Exercise	Description
Prone extension	The subject is prone with the shoulders resting in 90 of forward flexion. From this position, the subject performs bilateral extension to a neutral position with the shoulder in neutral rotation.
Forward flexion in side lying	The subject is in a side-lying position, with the shoulder in neutral. The subject performs 90 of unilateral forward flexion in a sagittal plane.
External rotation in side lying	The subject is side lying with the shoulder in neutral position and the elbow flexed 90. From this position, the subject performs 90 of external rotation of the shoulder with a towel between the elbow and trunk to avoid compensatory movements.
Prone horizontal abduction with external rotation	The subject is prone with the shoulders resting in 90 of forward flexion. From this position, the subject performs bilateral horizontal abduction to a horizontal position, with an additional external rotation of the shoulder at the end of the movement.

